13.2 Interferon Alpha-2b

Interferon Alpha-2b may cause fever, chills and flu-like symptoms; loss of appetite; nausea; vomiting, diarrhea and abdominal pain; fatigue; lowered white blood count may increase risk of infection; lowered platelets may lead to an increase in bruising or bleeding; hair loss. Other risks which may be common in cases of prolonged administration of Interferon Alpha-2b include drowsiness; temporary confusion; anxiety, amnesia, irritability, confusion, delusions and depression which can be severe; numbness and/or tingling in the hands and/or feet, skin rashes and inflammation of the pancreas. Inflammation of the pancreas is swelling or irritation of the pancreas which may result in tenderness or pain in the stomach and/or back. When the pancreas is inflamed, the body is not able to absorb all the nutrients it needs.

For more risk information reference the Investigator's Brochure or package insert.

13.3 Rintatolimod

Clinical experience with rintatolimod totals over 800 patients with more than 400 patients receiving Rintatolimod for at least six (6) months, greater than 200 patients for one (1) year, over 50 patients up to two (2) years, and with 20 or more patients over two (2) years at doses as high as 1200 mg i. v. twice weekly. No evidence of dose-limiting organ toxicity, including hematologic, liver, or renal toxicity, has been observed.

Adverse events related to infusion such as mild flu-like symptoms, transient headache, fever, myalgia, arthralgia, and fatigue/malaise which were seen, usually occur during the initial weeks of treatment and tend to subside on repeated administration. These side events were seen in Chronic Fatigue Syndrome patients, cancer patients, chronic hepatitis B infected patients and individuals infected with HIV at doses of 200 and 400 mg and higher. Patients that experience these minor side effects can continue on Rintatolimod and as noted, these signs and symptoms typically subside after several weeks of continued treatment. Specific symptoms of note include a flushing reaction, characterized by at least one occurrence of erythema of the face, neck and chest, which has been observed in approximately 10% of patients treated in various studies. Usually the flushing is both mild and transient and disappears with repeated dosing. Occasionally, it can be accompanied by a tightness of the chest, tachycardia, anxiety, shortness of breath, subjective reports of "feeling hot", diaphoresis and nausea. The reaction is usually infusion-rate dependent and can generally be controlled by slowing the infusion rate. An antihistamine (diphenhydramine hydrochloride) can be helpful in controlling and reducing the response in the occasional patient for whom the symptom persists. Other less frequently occurring adverse effects include nausea, diarrhea, itching, urticaria, bronchospasm, transient hypotension, photophobia, rash, bradycardia and transient visual disturbances. A severe unexpected local reaction to extravasation of rintatolimod (Ampligen®, Poly I:Poly C₁₂U) at the infusion site in the dorsum of the left hand was reported in a Chronic Fatigue Syndrome patient with chilblains. Several patients experienced liver enzyme level elevations while receiving Rintatolimod associated with chronic dosing over many weeks.

Rintatolimod has been dosed in combination with alpha interferon in investigator initiated studies under investigator IND applications during the period between December 1985 and April 1994. A total of 24 patients received combination treatments. Clinical conditions included renal cell carcinoma, chronic myelogenous leukemia, melanoma, and ovarian cancer. Rintatolimod was given as an IV infusion at a dose of 300 mg twice weekly. The starting dose was sometimes as low

PROTOCOL TITLE: Phase 2A Study Evaluating a Chemokine-Modulatory Regimen in Patients with Colorectal Cancer Metastatic to the Liver

as 1-10 mg. The interferons were administered at a dose of 3 million Units daily, with some doses of 0.75 million units at the low side and up to 6 million units at the higher side.

The therapy with rintatolimod in combination with alpha interferon was generally well tolerated without evidence of dose-limiting or cumulative toxicities. The most frequent adverse reactions were considered minor in severity and duration. Most of them were flu-like symptoms such as chills, cold feeling, fatigue, decreased appetite, fever, muscular aches. Also shortness of breath has been seen as well as hypotension, nausea, anemia, dyspnea, numbness, itching and blurred vision. These adverse events were judged possibly related to the condition of the patients, but also possibly related to the administration of rintatolimod or interferon. In some cases worsening of the patient's condition has been seen due to tumor progression, but in general favorable clinical patterns were observed in these patients with advanced disease. Such combinations were not intended to be immune modulating and were evaluated in the context of clinical cancer care.

For more risk information reference the Investigator's Brochure or package insert.

14 POTENTIAL BENEFITS TO SUBJECTS

Patients enrolled in this study have either been treated with standard therapies which provide substantial beneficial or are ineligible for or refusing such therapies. This treatment has potential to provide anti-tumor benefit (regression/stabilization). The probability of such a benefit is unknown.

15 DATA AND SPECIMEN BANKING

After processing, all samples for correlative analysis (blood and tissue) will be sent to [name] laboratory for storage and analysis (CCC, C-502). Samples will be used for planned study assays as well as for future analysis for other, yet to be identified biomarkers that may be related to clinical outcome. Any clinical data that is associated with the samples will be stored on a secured server in the Department of Medicine, will be accessible only by the PI, co-investigators and PI-designated data manager and, will be password protected. All computer entry and networking programs will be done using PIDs only.

Note: All investigator or analyzing research laboratories housing research samples need to maintain current Temperature Logs and study-specific Sample Tracking and Shipping Logs. The Principal Investigator/Laboratory Manager must ensure that the stated lab(s) have a process in place to document the receipt/processing/storage/shipping of study-related samples/specimens. This is required for both observational and interventional clinical studies collecting clinical samples.

16 MEASUREMENT OF EFFECT

16.1 Solid Tumors

Response and progression will be evaluated in this study using the new international criteria proposed by the revised Response Evaluation Criteria in Solid Tumors (RECIST) guideline (version 1.1) [Eur J Ca 45:228-247, 2009]. Changes in the largest diameter (unidimensional measurement) of the tumor lesions and the shortest diameter in the case of malignant lymph nodes are used in the RECIST criteria.

PROTOCOL TITLE: Phase 2A Study Evaluating a Chemokine-Modulatory Regimen in Patients with Colorectal Cancer Metastatic to the Liver

For the purposes of this study, patients should be re-evaluated for response on Day 46 (\pm 3 days). In addition to a baseline scan, confirmatory scans should also be obtained 8 weeks (not less than 4) weeks following initial documentation of objective response.

Please refer to Appendix G for a summary of tumor response assessment according to RECIST 1.1 criteria.

17 SAFETY EVALUATION

17.1 Adverse Events

17.1.1 Definition

An adverse event or adverse experience (AE) is any untoward medical occurrence associated with the use of a drug in humans, whether or not considered drug related. Therefore, an AE can be ANY unfavorable and unintended sign (including an abnormal laboratory finding), symptom, or disease temporally associated with the use of a medicinal (investigational) product, whether or not considered related to the medicinal (investigational) product (attribution of ‘unrelated’, ‘unlikely’, ‘possible’, ‘probable’, or ‘definite’).

An AE is considered “unexpected” if it is not listed in the investigator brochure or is not listed at the specificity or severity that has been observed; or if an investigator brochure is not required or available, is not consistent with the risk information described in the general investigational plan in other study-related documents.

- **Diagnosis Versus Signs and Symptoms**

If known, a diagnosis should be recorded on the CRF rather than individual signs and symptoms (e.g., record only liver failure or hepatitis rather than jaundice, asterixis, and elevated transaminases). However, if a constellation of signs and/or symptoms cannot be clinically characterized as a single diagnosis or syndrome at the time of reporting, each individual event should be recorded as an AE or SAE on the CRF. If a diagnosis is subsequently established, it should be reported as follow-up information.

- **Adverse Events Occurring Secondary to Other Events**

In general, AEs occurring secondary to other events (e.g., cascade events or clinical sequelae) should be identified by their primary cause. For example, if severe diarrhea is known to have resulted in dehydration, it is sufficient to record only diarrhea as an AE or SAE on the CRF.

However, clinically significant AEs occurring secondary to an initiating event that are separated in time should be recorded as independent events on the CRF. For example, if a severe gastrointestinal hemorrhage leads to renal failure, both events should be recorded separately on the CRF.

- **Abnormal Laboratory Values**

Only clinically significant laboratory abnormalities that require active management will be recorded as AEs or SAEs on the CRF (e.g., abnormalities that require study drug dose modification, discontinuation of study treatment, more frequent follow-up assessments, further diagnostic investigation, etc.).

PROTOCOL TITLE: Phase 2A Study Evaluating a Chemokine-Modulatory Regimen in Patients with Colorectal Cancer Metastatic to the Liver

If the clinically significant laboratory abnormality is a sign of a disease or syndrome (e.g., alkaline phosphatase and bilirubin 5 x the upper limit of normal associated with cholecystitis), only the diagnosis (e.g., cholecystitis) needs to be recorded on the Adverse Event CRF.

If the clinically significant laboratory abnormality is not a sign of a disease or syndrome, the abnormality itself should be recorded as an AE or SAE on the CRF. If the laboratory abnormality can be characterized by a precise clinical term, the clinical term should be recorded as the AE or SAE. For example, an elevated blood potassium level of 7 mEq/L should be recorded as “hyperkalemia”

Observations of the same clinically significant laboratory abnormality from visit to visit should not be repeatedly recorded as AEs or SAEs on the CRF, unless their severity, seriousness, or etiology changes.

- **Preexisting Medical Conditions (Baseline Conditions)**

A preexisting medical condition should be recorded as an AE or SAE only if the frequency, severity, or character of the condition worsens during the study. When recording such events on an Adverse Event CRF, it is important to convey the concept that the preexisting condition has changed by including applicable descriptors (e.g., “more frequent headaches”).

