8.2 Secondary Endpoints

- Objective response rate by RECIST v1.1
- Overall safety profile characterized by type, frequency, severity (according to CTCAE Version 4.0), timing, seriousness and relationship to study treatment

PROTOCOL TITLE: Phase 2A Study Evaluating a Chemokine-Modulatory Regimen in Patients with Colorectal Cancer Metastatic to the Liver

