10 TREATMENT

10.1 Dosing and Administration

10.1.1 Chemokine modulating regimen

For dosing, refer to Table 1. The chemokine modulating regimen will be administered on an outpatient basis at Roswell Park Cancer Institute over 3 consecutive days, every week x 3 weeks (Days 1, 2, 3, 8, 9, 10, 15, 16, 17) in the following order:

- Pretreatment: 500 mL Normal saline IV over 60 minutes
- Pre-meds: Acetaminophen (Tylenol) 650 mg by mouth x 1 dose; Prochlorperazine (Compazine) 10 mg by mouth x 1 dose – administered 30 minutes (\pm 5 minutes) after starting pre-treatment hydration

PROTOCOL TITLE: Phase 2A Study Evaluating a Chemokine-Modulatory Regimen in Patients with Colorectal Cancer Metastatic to the Liver

- Celecoxib: 200 mg orally, administered along with pre-meds
- Interferon Alpha-2b : (20 million units/M²) IV over 20 minutes
- Rintatolimod: 200 mg IV, initial administration should begin at a slow rate of infusion (approximately 20 cc/ hour) and increase to 40 cc/ hour after 30 minutes. Tubing should be flushed with 30 to 50 mL of normal saline solution upon completion. Administration will be followed by 1 hour of observation and vital signs at 30 and 60 minutes post infusion (\pm 5 minutes)
- Celecoxib: 200 mg orally to be taken by the patient at home approximately 12 hours following the initial dose.

Pretreatment and pre-meds listed above are recommendations and may be modified based upon institutional SOC requirements and at the discretion of the investigator. Treatment is intended for an outpatient setting. However, at the investigator's/physician's discretion, the participant may receive treatment as an inpatient, if deemed necessary.

Each 3 day treatment will be initiated after interval history and physical examination is performed and once the relevant laboratory studies have been confirmed to be within clinically acceptable ranges, specifically: ANC \geq 1000/mm³, total bilirubin \leq 1.5 x ULN or \leq 3 x ULN (for patients with Gilbert's Syndrome), AST and ALT $<$ 3 x ULN (or $<$ 150% of values at baseline). Treatment may be delayed up to 3 weeks to allow for resolution of any intercurrent illness or for logistical reasons. Delays beyond 3 weeks will require discussion with the study PI to review appropriateness of continuing therapy on study.

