10.2 Dose Modification

The following dose modification rules will be used with respect to potential toxicity. Toxicity will be assessed according to the NCI Common Terminology Criteria for Adverse Events Version 5.0 (CTCAE v5.0).

Therapy will be immediately discontinued for any grade IV treatment-related toxicity that becomes apparent. The exception to this is for grade 4 neutropenia of $<$ 7 days duration. Study treatment will be reinitiated for any grade treatment-related III toxicity pending the reversal of such toxicity after withholding treatment (i.e. the toxicity resolves to the subject's baseline level). In the event of any adverse effect, appropriate medical treatment will be instituted and study treatment will be discontinued if the above toxicity remains.

PROTOCOL TITLE: Phase 2A Study Evaluating a Chemokine-Modulatory Regimen in Patients with Colorectal Cancer Metastatic to the Liver

Table2. Treatment Related Toxicity Management

Treatment-related AEs	Toxicity grade or conditions (CTCAE5.0)	Action taken for Interferon Alpha-2b	Action taken for Rintatolimod	Action taken for Celecoxib	Additional actions
Chills/Fever	Grade 3	None	None	None	Consider additional acetaminophen dosing, supportive care
Pancreatitis	Grade 3	Hold Decreased future doses by 50%	Hold	Hold	Supportive measures as clinically indicated
AST / ALT elevation or Increased bilirubin	Grade 3	Hold until improved to grade 1; Decrease future doses by 50%	Hold	Hold	Advise evaluation for other possible etiologies; consider imaging
Vomiting	Grade 3	Hold until resolved to grade 1; Decrease future doses by 50%	Hold	Hold	
Neuropathy	Grade 2 or greater	Hold until decreased to patient's baseline; Decrease future doses by 50%	None	None	
Depression or other clinically relevant mood disorder	Grade 3	Permanently discontinue; appropriate supportive care/intervention	None	None	
Neutropenia	Grade 3 or greater	Hold until ANC > 1000; Decrease future doses by 50%	Hold	Hold	
Hemorrhage	Grade 2 or greater	None	None	Permanently discontinue	
Myocardial infarction or other arterial thrombotic event	Grade 2 or greater	None	None	Permanently discontinue	

PROTOCOL TITLE: Phase 2A Study Evaluating a Chemokine-Modulatory Regimen in Patients with Colorectal Cancer Metastatic to the Liver

Treatment-related AEs	Toxicity grade or conditions (CTCAE5.0)	Action taken for Interferon Alpha-2b	Action taken for Rintatolimod	Action taken for Celecoxib	Additional actions

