All other clinically significant AEs ¹	Intolerable Grade 2 or Grade 3	Hold therapy until resolved; reduce future doses by 50%	Hold therapy until resolved; reduce future doses by 50%	Hold therapy until resolved	
	Grade 4	Permanently Discontinue	Permanently Discontinue	Permanently Discontinue	
1. Holding of any therapies here for intolerable grade 2 or grade 3 toxicities will be at the discretion of the investigator based upon the nature of the AE and whether one drug can be clearly implicated or not; in the case that one drug can be clearly implicated, only that drug should be dose reduced in the future; in the case that the causative agent is unclear, it is recommended that interferon and rintatolimod are reduced as directed					

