10.2.1 Celecoxib Non-Hematologic Toxicities

Considered to be possibly, probably, or definitely related to Celecoxib (Interferon Alpha-2b and rintatolimod will be continued). See Table 2. Celecoxib will be discontinued for any attributable grade ≥ 2 toxicity, except for nausea, vomiting, or a similar readily manageable condition.

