10.2.2 Interferon Alpha-2b and/or rintatolimod Non-hematologic toxicities

Considered to be possibly, probably, or definitely related to Interferon Alpha-2b and rintatolimod:

- Interferon Alpha-2b :

For grade 3 toxicity:

- 1st episode: dose will be held and restarted at the next study visit at a dose reduction of 50%. The dose can be re-escalated if toxicity is reduced to \leq grade 1 or baseline.
- 2nd episode: Treatment will be discontinued

For grade 4 toxicity (except neutropenia of < 7 days duration):

- Treatment will be discontinued

- Rintatolimod:

For grade 3 toxicity:

- 1st episode: dose will be held and restarted at the next study visit at a dose reduction of 33%. The dose can be re-escalated if toxicity is reduced to \leq grade 1 or baseline
- 2nd episode: dose will be held and (if toxicity is resolved to \leq grade 1 or baseline) restarted at the next study visit at a dose reduction of 33%. The dose cannot be re-escalated

PROTOCOL TITLE: Phase 2A Study Evaluating a Chemokine-Modulatory Regimen in Patients with Colorectal Cancer Metastatic to the Liver

For grade 4 toxicity:

- Treatment will be discontinued

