It is anticipated that 15 patients will be enrolled to this study. The table above presents the minimum number of subjects experiencing treatment-related SAEs (i.e., those SAEs judged to be possibly, probably, or definitely related to the study regimen) that would dictate suspension of the trial in accordance with the stopping rule. Using these assumptions the trial will be suspended if:

- 2 subjects experience treatment related SAE among the first 2 subjects enrolled
- 3 subjects experience treatment related SAE among 3 – 5 subjects or,
- 4 subjects experience treatment related SAE among 6 – 7 subjects or,
- 5 subjects experience treatment related SAE among 8 – 10 subjects or,
- 6 subjects experience treatment related SAE among 11 – 12 subjects,
- 7 subjects experience treatment related SAE among 13 – 15 subjects.
- Any death not clearly due to the underlying disease or extraneous causes

At the completion of the study, all AEs will be summarized by weekly treatments and grade using frequencies and relative frequencies.

Treatment Related SAEs for Safety Monitoring

Treatment Related SAEs will be defined as the following events that occur during the period of Day 1 through the End of Treatment visit:

- \geq Grade 3 treatment-related non-hematologic toxicities, except:
 - The following grade \geq 3 toxicities (lasting <7 days)
Flu-like symptoms/constitutional symptoms (i.e., fever, chills, arthralgias, myalgias)
Depression, anxiety, restlessness, or insomnia
GI symptoms (i.e., nausea, diarrhea)
AST/ALT (unless accompanied by Grade 2 increased bilirubin)
 - Please note, if the above grade 3 toxicities last ≥ 7 days, they will be defined as a DLT
- \geq Grade 4 treatment related non-hematologic toxicity
- Hy's law criteria:

PROTOCOL TITLE: Phase 2A Study Evaluating a Chemokine-Modulatory Regimen in Patients with Colorectal Cancer Metastatic to the Liver

- An elevated alanine transaminase (ALT) or aspartate transaminase (AST) lab value that is greater than or equal to three times (3X) the upper limit of normal (ULN) and
- An elevated total bilirubin lab value that is greater than or equal to two times (2X) ULN and, at the same time, an alkaline phosphatase (ALP) lab value that is less than 2X ULN,
- As a result of within-protocol-specific testing or, unscheduled testing

Safety Review and Study Suspension

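### Scheduled laboratory changes that prompt no management reach no planned safety output; one descriptive worst-grade and shift table would close the gap (low priority)

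*Combined protocol and SAP*

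**What the plan says.** **Recording.** Section 17.1.1 (Abnormal Laboratory Values) states: "Only clinically significant laboratory abnormalities that require active management will be recorded as AEs or SAEs on the CRF". Its examples of active management are broad and open-ended: dose changes, stopping treatment, extra follow-up and further investigation.

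**Planned output.** Section 19.4 states that at study end "all AEs will be summarized by weekly treatments and grade using frequencies and relative frequencies". Section 19 contains no summary of laboratory values, no table of laboratory grades and no shift table.

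**Endpoint.** Section 8.2 lists as a secondary endpoint: "Overall safety profile characterized by type, frequency, severity (according to CTCAE Version 4.0), timing, seriousness and relationship to study treatment".

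**Schedule.** Section 11.1 and Appendix F place hematology and chemistry at screening, Days 1, 8 and 15, and the EOT visit. Chemistry includes ALP, AST, ALT, total bilirubin, amylase and lipase.

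**Rules that lead to action.**
- Section 10.1.1 lets each three-day block start "once the relevant laboratory studies have been confirmed to be within clinically acceptable ranges, specifically" for ANC, total bilirubin, AST and ALT.
- Section 10.2.1 adds "Celecoxib will be discontinued for any attributable grade ≥ 2 toxicity", apart from readily managed symptoms.
- For related grade 3 events, Section 10.2 says "Study treatment will be reinitiated for any grade treatment-related III toxicity pending the reversal of such toxicity after withholding treatment".
- For events without their own row in the toxicity table, its footnote says "Holding of any therapies here for intolerable grade 2 or grade 3 toxicities will be at the discretion of the investigator".

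**The concern.** The recording rule and the output rule filter in sequence. The first keeps a laboratory abnormality out of the AE data unless someone manages it. The second reports only AEs. The reported frequency of lower-grade laboratory toxicity therefore depends on what the investigator did as well as on the measured values.

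This matters because safety is a secondary objective, and 8.2 describes it by frequency and CTCAE severity. Section 19.4 notes that the earlier Phase I study gave a single cycle, so tolerability over three weekly blocks is the new question. Section 10.2.3 says the team will look for unexpected increases in four groups of toxicity. Two of them, myelosuppression and hepatotoxicity, show mainly in laboratory values. A drift in counts or liver tests over successive blocks could stay below every action level and leave no trace in the final tables.

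**Working it through.** The plan gives no figure to reproduce. The check follows a laboratory value from collection to output.

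**1. Panels after the first dose (11.1, Appendix F).**
- Day 8 follows block 1 (Days 1–3). Day 15 follows block 2 (Days 8–10). EOT follows block 3 (Days 15–17).
- EOT window: 29 − 10 = Day 19 to 29 + 10 = Day 39, after the last planned dose on Day 17. The Day 20 biopsy visit has no laboratory panel.
- So 1 of 3 post-dose panels can show the effect of block 3, and no pre-dose check or dose hold remains at that point.
- With 15 patients, at most 15 × 3 = 45 hematology and 45 chemistry panels after the first dose.

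**2. Routes by which a value reaches an output.**

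| Route | What it carries |
|---|---|
| 10.1.1 pre-dose check, Days 1, 8, 15 | ANC below 1000; bilirubin above 1.5 × ULN (3 × for Gilbert's syndrome); AST/ALT at or above 3 × ULN unless below 150% of baseline. Attribution is irrelevant. A failed check delays treatment, which I count as active management. |
| 10.2, 10.2.2 and the toxicity table | Related grade 3 withheld, related grade 4 stopped; neutropenia held from grade 3 |
| 10.2.1 | Grade 2 or higher non-hematologic toxicity at least possibly related to celecoxib |
| Catch-all row of the toxicity table | Intolerable grade 2 and grade 3, at the investigator's discretion |
| 19.4 monitored events, Day 1 to EOT | Related grade 3 or higher non-hematologic toxicity (with short-duration exceptions) and Hy's law values |
| 17.1.1 | Anything that prompts extra follow-up, work-up or treatment |

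The routine reporting table in 17.2 is not a further route. It sorts events by grade and attribution once they are AEs, and 17.1.1 decides that first.

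**3. What has no route.**
- *Grade 1 changes* that nobody acts on.
- *Grade 2 chemistry changes that pass, or are outside, the pre-dose check.* ALP, amylase and lipase are not in it. AST/ALT passes below 3 × ULN. Entry allows 2.5 × ULN, so a patient at that ceiling still passes up to just under 2.5 × 1.5 = 3.75 × ULN.
- *Blood counts below an action level.* Entry requires ANC of at least 1500 and the pre-dose check at least 1000, so 1000–1499 is below entry and prompts nothing. Platelets and hemoglobin are not in the check and have no row of their own. The 19.4 monitored list names no hematologic events.
- *Lower-grade EOT values* with no follow-up ordered.

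**4. Size.** One omitted patient changes a reported rate by 1/15 = 0.067, or 6.7 percentage points. The number omitted cannot be derived: the documents give no expected lower-grade laboratory rates and do not print the CTCAE cut-offs.

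**The case against.** The strongest reply is that this is a deliberate and common convention with a low threshold: one extra blood draw makes an abnormality recordable. What stays out is what the investigator considered not clinically significant or not in need of action. Seriousness and relationship, both named in 8.2, are attributes of AEs rather than of raw values, so an AE summary fits the endpoint. The monitoring in 10.2.3 is carried out through the stopping rule, with emphasis on higher grades, and does not promise a table of grade 1–2 values. EOT liver values would also be hard to read, since they usually follow a multi-core liver biopsy in patients with liver metastases.

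Most of this stands and limits the point. It does not remove it: 8.2 also asks for frequency and CTCAE severity, and for laboratory toxicity at the lower grades the plan obtains these only where someone acted.

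A reader might infer more than the documents support:
- **That every grade 2 non-hematologic change not attributed to celecoxib goes unreported.** It does not. Liver values failing the pre-dose check delay treatment whatever the attribution, and intolerable grade 2 events can lead to a hold. Attribution to celecoxib needs only to be possible, and all three drugs are given on the same days.
- **That every EOT value without work-up is lost to the report.** Related grade 3 or higher non-hematologic toxicity and Hy's law values count under 19.4 through EOT. Whether a grade 3 AST/ALT rise lasted 7 days can be settled only by repeat testing, which is itself recordable.
- **That the stopping rule misses events because of 17.1.1.** Section 19.4 defines monitored events by grade, relatedness and laboratory values, with no management condition.

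**Conclusion.** The point holds in limited form. Liver values that fail the 10.1.1 check, Hy's law cases, related grade 3 or higher non-hematologic toxicities under 19.4, and changes leading to a hold or work-up are all captured. Other scheduled laboratory changes that prompt no management enter no planned output. The four residual groups in the working are the extent of it.

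This is a gap in planned reporting for a secondary endpoint. The values are collected, no decision rule changes, and the size of the under-count is unknown. The conclusion assumes that a treatment delay counts as active management, and that severe count falls at EOT would in practice prompt a repeat count. I rate it a cheap improvement of low priority.

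**What to change.** In 19.4 add, for the safety analysis cohort, one descriptive table giving:
- the worst post-baseline CTCAE v4.0 grade per patient (the version in 8.2 and 17.2; Section 10.2 uses v5.0, so state it in the title);
- the shift from baseline grade to worst grade;
- for ALT, AST, total bilirubin, ALP, amylase, lipase, ANC, platelets and hemoglobin.

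Derive it from all scheduled and unscheduled values, whether or not an AE was recorded, with baseline as the last value before the first dose. The shift is needed because entry allows AST/ALT up to 2.5 × ULN, hemoglobin down to 9 g/dL and platelets down to 75,000/μL. Label the table descriptive: with one arm, disease progression and the Day 20 liver biopsy may contribute to EOT liver values. While editing, correct the pointer in 19.3 from Section 9.4 to 19.4.

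The cost is one extra table, with no new visit, sample or test. Reported laboratory toxicity may look slightly less favourable.
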